8.3 SURGICAL TECHNIQUE

The operative visit of this study is retrospective. The use of the Q-Fix™ All-Suture Anchor System was performed per standard of care at the participating study sites.

9. SUBJECT ENROLLMENT AND WITHDRAWAL

9.1 SUBJECT POPULATION

To eliminate the potential for bias, Investigators will consecutively screen subjects by date of surgery, starting with subjects that have undergone arthroscopic or open soft tissue repair with Q-Fix™ All-Suture

CONFIDENTIAL AND PROPRIETARY

This document contains information that is confidential and proprietary to Smith & Nephew PLC and Smith & Nephew, Inc. and is intended for use only by Smith & Nephew and its manufacturer. It shall not be reproduced or copied in whole or in part, nor shall the contents be disclosed by any means without prior written permission from Smith & Nephew, nor shall anyone make any use of it that is contrary to the expressed or implied wishes of Smith & Nephew.

Study Protocol—Device	
Safety and Performance of Q-Fix™ All-Suture Anchor System	Number: 17-5010-11
	Version: 2.0 05SEP2019
	Page: Page 19 of 62

Anchor system in the past 12 months as of the IRB approval date, or using another date as agreed upon by the Investigators and site. In addition, to ensure enrollment of Q-Fix™ MINI subjects, a different enrollment start date may be selected to enroll Q-Fix™ MINI subjects only.

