9.3 EXCLUSION CRITERIA

Any one (1) of the following criteria will disqualify a potential subject from participation in the study:

1. Subject is ≤ 6 months post-operative
2. Subject is entered in another investigational drug, biologic, or device study or has been treated with an investigational product within 12 months post-operative.

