10.3.2 Retrospective Consecutive Enrollment

To minimize any potential for selection bias consecutive enrollment will be utilized to retrospectively enroll any subjects encountered that meet the inclusion/exclusion criteria.

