23.3 PROTOCOL AMENDMENT #1

- **General Purpose**

The purpose for this amendment is to:

- 1) Decrease age limit to ≥ 13 years to include adolescents as it was determined that the Q-Fix™ anchor is being used by sites in adolescents; it is important to obtain information on the safety and performance in the adolescent population as well as in adults. A secondary objective is added so that an analysis may be done on adolescents and young adults ages 13-21 years of age. As this retrospective study is granted a waiver of informed consent for adults, it is requested for adolescents as well.
- 2) Increase enrollment maximum to 450 subjects to allow for the enrollment of adolescents and additional Q-Fix™ MINI subjects (150 maximum per joint type.)
- 3) Revise the timeline to account for the enrollment of adolescents; this amendment is not expected to affect the overall study duration.
- 4) Include both open and arthroscopic surgeries in the study as it was determined that sites used the Q-Fix™ anchor in both arthroscopic and open soft tissue repair surgeries; it is important to obtain safety and performance data for both types of surgery. Also clarified that as the study is collecting real world safety data, use in knee, shoulder, and hip may be collected beyond the indications for use.
- 5) Clarify that another enrollment date may be used if agreed upon by Investigators and site, as long as a bias is not introduced using this date. In addition, the enrollment start date for Q-Fix™ MINI may be different than the start date for the 1.8 and 2.8mm Q-Fix™ anchors to ensure that the data is collected on all 3 sizes of the Q-Fix™ anchor.

- **Rationale**

The rationale for the changes is as follows:

- 1) From the screening and enrollment logs provided by the sites to the Sponsor, individuals <18 years old are receiving Q-Fix™ anchors, but this population is not included per the current

CONFIDENTIAL AND PROPRIETARY

This document contains information that is confidential and proprietary to Smith & Nephew PLC and Smith & Nephew, Inc. and is intended for use only by Smith & Nephew and its manufacturer. It shall not be reproduced or copied in whole or in part, nor shall the contents be disclosed by any means without prior written permission from Smith & Nephew, nor shall anyone make any use of it that is contrary to the expressed or implied wishes of Smith & Nephew.

Study Protocol—Device	
Safety and Performance of Q-Fix™ All-Suture Anchor System	Number: 17-5010-11

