This document contains information that is confidential and proprietary to Smith & Nephew PLC and Smith & Nephew, Inc. and is intended for use only by Smith & Nephew and its manufacturer. It shall not be reproduced or copied in whole or in part, nor shall the contents be disclosed by any means without prior written permission from Smith & Nephew, nor shall anyone make any use of it that is contrary to the expressed or implied wishes of Smith & Nephew.

Study Protocol—Device	
Safety and Performance of Q-Fix™ All-Suture Anchor System	Number: 17-5010-11
	Version: 2.0 05SEP2019
	Page: Page 56 of 62

IRB approval date.” Biostatisticians confirmed that the goal of that statement was to ensure that sites were not selecting records to prevent bias, and therefore this was broadened to include that a start date may be agreed upon by the Site and Sponsor. In addition, as the Q-Fix™ MINI anchor was released later than the 1.8mm and 2.8mm Q-Fix™ anchors, to ensure enrollment of MINI anchors, a more recent date will need to be used by the sites to specifically target Q-Fix™ MINI subjects.

- **Effect on Study Status**

These changes does not affect subjects that are already enrolled and does not affect the Case Report Forms. Current enrollment is 106 hip subjects, 99 shoulder subjects, and 24 knee subjects across all 5 sites that are participating in the study. If approval is received to enroll adolescents, the Statistical Analysis Plan will be revised to include adolescents to reflect the change in Secondary Endpoints. This change is not expected to affect the overall timeline of 2.5 years, however, enrollment is expected to require 16 months rather than 12 months and follow-up was decreased from 6 months to 2 months.

CONFIDENTIAL AND PROPRIETARY

This document contains information that is confidential and proprietary to Smith & Nephew PLC and Smith & Nephew, Inc. and is intended for use only by Smith & Nephew and its manufacturer. It shall not be reproduced or copied in whole or in part, nor shall the contents be disclosed by any means without prior written permission from Smith & Nephew, nor shall anyone make any use of it that is contrary to the expressed or implied wishes of Smith & Nephew.

Study Protocol—Device	
Safety and Performance of Q-Fix™ All-Suture Anchor System	Number: 17-5010-11
	Version: 2.0 05SEP2019
	Page: Page 57 of 62

■ **Details**

Section	Current Text 26JUN2018 Version 1.0	Revised Text 05SEP2019 Version 2.0

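### Protocol 9.1 lets the investigator and site set another enrolment start date with no sponsor agreement, bias condition or timing rule, which weakens the consecutive-enrolment safeguard

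*Protocol*

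**What the plan says.** Protocol 9.1 opens with the safeguard: "To eliminate the potential for bias, Investigators will consecutively screen subjects by date of surgery". The default anchor is surgery "in the past 12 months as of the IRB approval date". The section then allows a start "using another date as agreed upon by the Investigators and site", and for the MINI anchor says that "a different enrollment start date may be selected to enroll Q-Fix™ MINI subjects only". It names nobody who decides the MINI date.

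Protocol 10.3.2 relies on the same device: "To minimize any potential for selection bias consecutive enrollment will be utilized".

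Amendment #1 (Protocol 23.3) explains the change in two places. Item 5 of the general purpose repeats the investigators-and-site wording but adds a condition: "as long as a bias is not introduced using this date". Item 5 of the rationale says that "a start date may be agreed upon by the Site and Sponsor", and that the aim was to stop sites selecting records. It also says that the sites had found the wording then in force confusing. The SAP has no rule on the start date.

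**The concern.** Consecutive screening protects against selection only if the starting point does not depend on outcome. In this study outcomes can be known beforehand. Protocol 9.3 excludes anyone for whom "Subject is ≤ 6 months post-operative", so most of the period that determines the primary endpoint has passed before a subject can be enrolled. Protocol 9.4 expects that some re-interventions will be found at screening. A surgeon who recalls a poor run of cases could start after it, or start earlier and reach the enrolment limit before it, and still screen consecutively.

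The study is uncontrolled, and its main result is a proportion with an exact 95% interval (Protocol 12.3.1, SAP 7.9.1). That interval describes sampling error only. It would not widen or shift if the start date had been chosen favourably.

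**Working it through.** **The plan's own figures.** Protocol 13 asks for 84 evaluable subjects, 28 per joint, at 5% loss. 28/0.95 = 29.5, rounded up to 30, and 3 × 30 = 90, as stated. This point changes no sample-size figure.

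**The texts side by side.**

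| Feature | Protocol 9.1 | Amendment #1, item 5 |
|---|---|---|
| Who agrees the date | Investigators and site | Purpose: investigators and site. Rationale: site and sponsor |
| Condition about bias | None for the alternative date | Purpose: yes |
| Date fixed before chart review | Not required | Not required |
| MINI-only date | Allowed, no decision-maker named | Allowed, because MINI was released later |

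The point rests on the 9.1 column alone. The amendment column shows the intent, and that 9.1 does not carry it.

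**How many subjects could be affected.** Inputs are enrolment at the amendment (106 hip, 99 shoulder, 24 knee; Protocol 23.3) and the limits of 30 to 150 per joint (synopsis).

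- Already enrolled: 106 + 99 + 24 = 229.
- Ceiling on later enrolment: 450 − 229 = 221, and 221/450 = 49%.
- By joint, at the maximum: hip 44/150 = 29%; shoulder 51/150 = 34%; knee 126/150 = 84%.
- At the knee minimum: 30 − 24 = 6, and 6/30 = 20%. Later enrolment is a majority of knee subjects only if the knee total exceeds 48.

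**What avoiding two re-interventions would do.** With n fixed, replacing two failures by two successes moves the rate by 2/n.

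- Overall, if only the knee is brought to its minimum: n = 229 + 6 = 235, and 2/235 = 0.9 points.
- Overall at the maximum: 2/450 = 0.4 points.
- In a small subset: the documents do not give the number of MINI subjects. If it is assumed to be 30 to 100, the shift is 2/30 = 6.7 down to 2/100 = 2.0 points.
- Knee at 30: only six subjects would come after the change. At the plan's assumed 5% failure rate the expected number of failures among six is 6 × 0.05 = 0.3. The chance of two or more is 1 − 0.95⁶ − 6 × 0.05 × 0.95⁵ = 1 − 0.735 − 0.232 = 0.03.

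**The mechanism, as a worst case.** A simulation assumed true success of 95%, independent outcomes and a start freely chosen with all outcomes known. For 30 consecutive subjects, mean observed success rises from 95.0% to 98.0%, 99.1% or 99.7% when the best start is taken from a series of 60, 90 or 150 cases. For 90 subjects from a series of 180 it rises to 97.1%. At a 5% failure rate the average gain cannot exceed 5 points. The series lengths are assumptions, since the documents give no site volumes. No joint here is a fresh sample of 30, so these are not estimates for this study.

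**The case against.** The best defence is that the amendment is part of the same protocol version. It states the no-bias condition and, in its rationale, the sponsor's role, so the 9.1 wording looks like a drafting slip and not a decision to give one party control. That is probably right about intent. But sites work from 9.1, and the amendment does not settle who agrees, because its purpose and rationale differ. Neither part says when the date must be fixed.

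Several other safeguards stand. Screening from the chosen date must still be consecutive. All screened subjects are logged with reasons for exclusion, and a re-intervention does not make a subject ineligible (Protocol 9.4), so failures cannot properly be dropped within the screened series. The sponsor receives the logs and monitors the sites. The log need not, however, show a period that was never opened. The MINI date has a reason unrelated to outcome, the later release. The adolescents for whom the maximum was partly raised were already on the screening logs, so a free start date does not select them.

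A reader might infer that no analysis could reveal the problem. That goes too far: the surgery date is on the Operative Data CRF (SAP 7.4.1), so subjects outside the default window can be identified and rates compared by period and site. This cannot recover patients who were never screened, but it can give warning.

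A reader might also infer a bias of six to seven points from two failures in a 30-subject joint sample. No joint's enrolment at the amendment fits that. Hip and shoulder are near 100 each, and 24 of the minimum 30 knee subjects were already enrolled.

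**Conclusion.** The point holds as a weakness in the operative wording. Section 9.1 lets a party that may know the outcomes choose where the consecutive series begins, without the sponsor agreement and no-bias condition that the protocol gives elsewhere for the same change. This weakens the consecutive-enrolment safeguard in 9.1 and 10.3.2 but does not remove it.

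The size of any bias is unknown. The 221 subjects are a ceiling. The effect on the overall rate is likely to be small: about 0.9 points for two avoided re-interventions at 235 subjects. It could be larger only in small joint or MINI subsets, where the figure depends on subset sizes that the documents do not give. The documents do not support reading the clause as evidence that any site chose its date by outcome, or that the sponsor meant to allow it. The endpoint is descriptive, with no performance goal to pass, so what is at risk is the credibility of the reported rate. The correction should be made because it is cheap and matches the stated intent.

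**What to change.** Reword 9.1 along these lines: any start date other than the default, including a MINI-only date, is agreed in writing by the sponsor and the site before charts from that period are opened and without reference to outcomes; screening is then consecutive from that date. The MINI date may be tied to the anchor's release or its availability at the site. Align item 5 of the amendment's purpose and rationale with this text.

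In the report, list each site's start date and the reason for it, including dates already used.

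In the SAP, add a repeat of the primary analysis restricted to subjects whose surgery fell within the 12 months before that site's IRB approval. Describe it as a partial check, since it cannot recover periods never screened.

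The cost is one protocol sentence, a dated note per site, one extra table and slightly less flexibility for sites. The sample size does not change.

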12.3 EFFICACY ANALYSIS

12.3.1 Analysis of Primary Endpoint(s)

CONFIDENTIAL AND PROPRIETARY

This document contains information that is confidential and proprietary to Smith & Nephew PLC and Smith & Nephew, Inc. and is intended for use only by Smith & Nephew and its manufacturer. It shall not be reproduced or copied in whole or in part, nor shall the contents be disclosed by any means without prior written permission from Smith & Nephew, nor shall anyone make any use of it that is contrary to the expressed or implied wishes of Smith & Nephew.

Study Protocol—Device	
Safety and Performance of Q-Fix™ All-Suture Anchor System	Number: 17-5010-11
	Version: 2.0 05SEP2019
	Page: Page 30 of 62

Clinical success rate, defined as subjects without re-intervention at 6 months post-operative, as assessed by the surgeon:

The frequency of the subjects without re-intervention at 6 months together with percentage with a 95% CI will be reported. Clinical success rate for the entire sample, as well as by the position (i.e. the hip, shoulder and knee will be reported). This analysis will be carried out using the per protocol population as the primary analysis population with the safety population used for sensitivity analysis.

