##### 5.4 Exploratory Endpoints

- Clinical success rate as defined above, by anchor size

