## 7.9 Evaluation of Efficacy

### 7.9.1 Analysis of Primary Endpoint

- Overall clinical success rate at 6 months will be summarized using count (n) and percentage (%). A 95% Confidence Interval (CI) for the percentage of subjects with clinical success at 6 months will be computed using exact methods. This same analysis will be repeated by the position, i.e. the hip, shoulder and knee will be reported. These analyses will be carried out using the per protocol population as the primary analysis population with the safety population used for sensitivity analyses.

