### 7.9.3 Exploratory Analysis

- Clinical success rate at 6 months and at 12 months for all subjects will be analyzed by anchor size.

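### An optional MINI-only enrolment stream is pooled with the all-size consecutive series in the primary rates, and success by anchor size is specified without joint, so the primary rates depend on an unspecified MINI share and the size rates may be confounded

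*Protocol*

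**What the plan says.** **Enrolment.** Protocol 9.1 has investigators screen consecutively by date of surgery to prevent bias. It then permits a second route: "a different enrollment start date may be selected to enroll Q-Fix™ MINI subjects only". The eligibility criteria in 9.2 and 9.3 do not mention anchor size. Protocol 10.3.2 carries no exception for this route: "consecutive enrollment will be utilized to retrospectively enroll any subjects encountered that meet the inclusion/exclusion criteria".

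**Purpose.** Amendment 1 (Protocol 23.3) explains that the MINI was released later than the 1.8 mm and 2.8 mm anchors and that data on all three sizes are wanted, so "a more recent date will need to be used by the sites to specifically target Q-Fix™ MINI subjects". The same amendment raises the ceiling partly for this purpose: "Increase enrollment maximum to 450 subjects to allow for the enrollment of adolescents and additional Q-Fix™ MINI subjects (150 maximum per joint type".

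**Primary analysis.** Protocol 12.3.1 reports "Clinical success rate for the entire sample, as well as by the position". SAP 7.9.1 follows: "This same analysis will be repeated by the position, i.e. the hip, shoulder and knee will be reported". Neither document separates, weights or caps the MINI-only subjects. SAP 7.11 lists no change of method.

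**Size analysis.** SAP 5.4 lists as exploratory "Clinical success rate as defined above, by anchor size". SAP 7.9.3 adds only this: "Clinical success rate at 6 months and at 12 months for all subjects will be analyzed by anchor size". SAP 7.4.3 gives no derivations for exploratory endpoints, so a subject with anchors of two sizes has no assigned row.

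**The concern.** A MINI-only pass selects on device size. At the surgery dates it covers, a 1.8 mm or 2.8 mm subject who meets every criterion is not taken unless the all-size series also reaches that date. Fixing the MINI start date firmly in advance would not remove this, because the selection is on the device and not on the date.

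Two things are at stake. First, the overall and per-joint success rates become averages over a size mix that sites can influence, while 10.3.2 invites the reader to take the sample as consecutive. The confidence interval does not show that dependence. Second, recruitment was changed so as to learn about the MINI, but the one planned analysis of success by size does not mention joint. A gap between sizes could reflect the joints in which each size is used, or the later surgery dates of the MINI subjects. A real difference could be hidden in the same way.

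**Working it through.** **The plan's own figures (Protocol 13, SAP 6.1).** With 28 evaluable per joint and 5% loss, 28 / 0.95 = 29.5, rounded up to 30; 3 × 30 = 90, as stated. The stated precision of 11% fits one joint: the exact 95% half-width at n = 28 is 9.1 points for 27/28 and 11.3 points for 26/28. For the pooled 84 it is about 5 points (5.2 for 80/84). No part of this calculation involves anchor size or stream.

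**Ceiling on the MINI-only share.** Inputs are enrolment at Amendment 1 (106 hip, 99 shoulder, 24 knee; total 229) and the maximum of 150 per joint. I assume that none of the 229 came through the MINI-only route, since that amendment introduced it.

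| Joint | Room left | Share of 150 |
|---|---|---|
| Hip | 150 − 106 = 44 | 29% |
| Shoulder | 150 − 99 = 51 | 34% |
| Knee | 150 − 24 = 126 | 84% |
| All | 221 of 450 | 49% |

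These are upper bounds. Adolescents and further all-size subjects use the same places, and the lower bound is 0.

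**Effect on the primary rate.** Pooled rate = (1 − w) × p_consecutive + w × p_MINI-only, so the shift is w × (p_MINI-only − p_consecutive). The documents give no size-specific rates. I take 95% for the consecutive stream (the plan's overall assumption) and assume 90%, 95% or 98% for the MINI-only stream.

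| w | 90% | 95% | 98% |
|---|---|---|---|
| 10% | 94.5% | 95.0% | 95.3% |
| 25% | 93.8% | 95.0% | 95.8% |
| 49% (ceiling) | 92.5% | 95.0% | 96.5% |

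At the ceiling the shift runs from −2.5 to +1.5 points. The exact half-width at n = 450 (428/450) is 2.1 points. For the knee at its ceiling the range is 0.84 × (−5) = −4.2 to 0.84 × 3 = +2.5 points. At equal success the shift is zero for every w.

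**Effect on the size rates.** Assume no size effect within any joint and put the other sizes at the 106/99/24 mix. With assumed hip/shoulder/knee success of 98/95/90%:

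- Other sizes: (106 × 0.98 + 99 × 0.95 + 24 × 0.90) / 229 = 95.9%.
- MINI at the mix of remaining room: (44 × 0.98 + 51 × 0.95 + 126 × 0.90) / 221 = 92.7%, a crude difference of −3.1 points before rounding.
- MINI all in the hip: 98.0%, a difference of +2.1 points.
- MINI at the same joint mix as the others: 0.

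With 97/95/93% the three differences are −1.5, +1.3 and 0 points. With equal joint rates they are all 0. The difference within each joint is 0 throughout, which is what a size-by-joint table would show.

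**The case against.** The strongest reply is that the MINI stream is a disclosed and reasoned choice. The anchor came to market later, the study exists to fill data gaps, and the route is optional. That stands, and the point does not ask for the stream to be dropped.

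Several further objections hold in part:

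- **The overall rate was never free of mix.** Joint numbers may run from 30 to 150 each. True, but the per-joint rates deal with that; they do not deal with size mix within a joint.
- **The size table already shows how MINI subjects fared.** Only in part. Subtracting all MINI subjects would also remove those who belong to the consecutive series, the subtraction is not available by joint, and subjects with two sizes have no row.
- **The ceilings are worst cases.** Agreed. For the hip, even 44 MINI-only subjects at assumed success of 85%, 90% or 100% beside 106 at 96% give pooled rates of 92.8%, 94.2% or 97.2%, all inside the exact interval for 144/150 (91.5% to 98.5%).
- **SAP 7.9.3 may not intend to ignore joint.** Its reference to all subjects may only contrast with the age 13 to 21 analysis, and the table shells said to accompany the SAP are not among the documents. The text is silent on joint; that is a gap in specification, not a declared rule.

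A reader might go further and infer that the size rates are confounded by joint, or that the plan compares sizes. The documents support neither. Confounding by joint needs size use and success both to differ by joint, and no such counts or rates are given. The size analysis is exploratory, with no test, contrast or margin. The one documented difference between the streams is the MINI's more recent start date.

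**Conclusion.** The point holds as a low-severity improvement. The MINI-only route departs from the enrolment described in Protocol 10.3.2, and its subjects enter the overall and per-joint primary rates unmarked. Those rates depend on a MINI share that the plan leaves open between 0 and the ceilings shown. The exploratory size rates may be confounded by joint and by surgery date.

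The size of either effect cannot be determined from the documents. The shifts of −2.5 to +1.5 points overall, and the spurious size differences of −3.1 to +2.1 points, rest on assumed success rates and joint mixes. They show that the effects could be of the order of the sampling error, not that they will be. Dependence on the MINI share has no effect if success does not differ by size. Confounding by joint vanishes if success, or the joint mix of the sizes, does not differ. It would also be too strong to say that the SAP presents the pooled rate as that of a consecutive series: it calls the study a retrospective case series, and the consecutive claim sits in the enrolment sections of the protocol.

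**What to change.** 1. **Flag the stream.** Record for each subject whether enrolment was through the all-size consecutive series or the MINI-only route. A MINI subject whose surgery date lies within the site's all-size consecutive window belongs to the consecutive stream; only the other MINI subjects are MINI-only. This requires the first and last surgery dates of each site's all-size series. Protocol 9.1 states no end date for that series, and the screening log in 9.4 is not required to show the stream.
2. **SAP 7.9.1.** Report the overall and per-joint primary rate, with exact interval, for the all-size consecutive stream beside the pooled rate. Describe only the former as a consecutive series, and qualify Protocol 10.3.2 to match.
3. **SAP 7.9.3.** Tabulate success by anchor size within joint, with subjects who received more than one size in their own row. Show surgery dates by size and note the difference when the table is read.

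The cost is one derived flag, two dates per site and SAP wording before database lock, with no new subjects or visits. The downside is a smaller n for the consecutive-stream rate and small cells in the size table: three sizes plus a mixed row across three joints make up to 12 cells, which is acceptable in an exploratory summary.
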